4.1.1 Analysis time points

4.1.1.1 Study Day and Period Day for listings

There is no Study or Period Day 0. For the purpose of the study participant data listings, Study Day and Period Day will not be calculated if the event/measurement date is partial. Instead, Study Day and Period Day will be presented as ‘--’ in the relevant study participant data listing.

Study Day for an event or measurement occurring before the date of the first dose will be calculated as follows:

$$\text{Study Day} = (\text{Event/Measurement Date} - \text{Date of First Dose})$$

Study Day for an event or measurement occurring on the date of the first dose is 1. Study Day for an event or measurement occurring on or after the date of the first dose to the date of the last dose will be calculated as follows:

$$\text{Study Day} = (\text{Event/Measurement Date} - \text{Date of First Dose}) + 1$$

For events or measurements occurring after the date of the last dose, Study Day will be prefixed with '+' in the data listings and will be calculated as follows:

$$\text{Study Day} = + (\text{Event/Measurement Date} - \text{Date of Last Dose})$$

In addition, a variable for Period Day will be defined for each Period based on the date of the single dose in each Treatment Period. Period Day will range from Day -1 to Day 41.

For the purpose of calculating the relative Day within each Period, the day before dosing in Treatment Period 1, and the washout period between the first and last dose are calculated relative to the first dose. Similarly, the day before dosing in Treatment Period 2, and the days between this dose and the EOS visit, are calculated relative to the last dose. If a study participant withdraws from the study early, the days between the last dose received and the Early Termination Visit (ETV) are calculated from the last dose they received and will be in either Treatment Period 1 or Treatment Period 2.

4.1.1.2 Analysis periods

The analysis periods consist of:

- Screening Period (Study Day -35 to -2).
- Treatment Period 1 consists of 36 days (Period Day -1 to 35).
- Washout Period consists of 7 days and occurs between the end of Treatment Period 1 and the start of the In-Clinic Period in Treatment Period 2 (i.e. between Treatment Period 1 Day 35 and Treatment Period 2 Day -1).
- Treatment Period 2 consists of 36 days (Period Day -1 to 35).

A study participant is defined as having started a Treatment Period if they receive a sc injection containing a single dose of ZLP in that period.

A study participant is considered to have completed Treatment Period 1 if they are not withdrawn from the study between Treatment Period 1 Day 1 and Treatment Period 2 Day -1, which includes the Washout Period. A study participant is considered to have completed Treatment Period 2 if they are not withdrawn from the study between Treatment Period 2 Day 1 and Treatment Period 2 Day 35.

End of study (EOS) procedures will be performed on the last sampling day (Day 35) of Treatment Period 2, in addition to the Day 35 procedures. Study participants who prematurely withdraw from the study will return to the study center for the Early Termination (ET) Visit as soon as possible after the time of withdrawal and will have all Day 35 (ie, Day 35 of the Treatment Period in which they withdrew from the study) and EOS procedures performed.

A study participant is considered to have completed the study if they have completed all periods of the study, including Treatment Period 1 and Treatment Period 2, and the EOS Visit assessments. Study participants have both Day 35 and EOS procedures performed on the last sampling day (Treatment Period 2 Day 35). Since Day 35 is part of Treatment Period 2, those who have completed the study have also completed all the required treatments and procedures.

The end of the study is defined as the date of the last EOS Visit for the last participant in the study.

4.1.2 **Definition of Baseline values**

In the protocol, the Baseline visit is defined as the first day of the first In-Clinic Period (Day -1). Baseline for the study is defined as the last non-missing measurement collected at the first day of the first In-Clinic Period (Day -1) for both Treatment Periods.

Endpoint-specific Baseline definitions are presented in [Table 4-1](#). Scheduled or unscheduled measurements may be used as the Baseline value.

Table 4-1: Definition of Baseline

Endpoint	Definition of Baseline
Hematology, clinical chemistry, urinalysis	Baseline for each treatment period is defined as the value on Day -1 of the respective treatment period. If these values are missing or multiple assessments occur, the last measure prior to dosing on Day 1 in each treatment period will be used as Baseline for that treatment period. Baseline for the EOS/ET visit assessment is defined as the Screening assessment. Note: No assessments for these endpoints are scheduled on Day 1 prior to dosing in both treatment periods. If an unscheduled sample is taken on Day 1 prior to dosing in either treatment period, this will be considered as the Baseline value for that treatment period.
Vital signs	Baseline is defined as the value (or mean value if measurement is taken in triplicate) on Treatment Period 1 Day -1. If this value is missing or multiple assessments occur, the last measure prior to dosing in Treatment Period 1 will be used as Baseline.

4.1.3 **Mapping of assessments performed at Early Termination Visit**

Unscheduled measurements performed for the ET Visit will be assigned to the EOS Visit and analyzed accordingly as an EOS Visit.

4.1.4 **Treatment assignment**

Treatment assignment for the SS and PKS will be according to the actual treatment received.

4.1.5 **Multicenter studies**

This is a single center trial.

4.1.6 Handling repeated and unscheduled measurements

Repeated and unscheduled measurements will be presented in the data listings. Repeated measurements are defined as more than 1 measurement at the same visit. The following general rules will apply to all repeated and unscheduled measurements:

- For repeated measurements obtained prior to the single dose of study treatment within each treatment period, the latest value (which may be scheduled or unscheduled) will be used in the calculation of the descriptive statistics.
- For repeated measurements obtained at the time of the designated Baseline measurement (see [Table 4-1](#)) the latest value (which may be scheduled or unscheduled) will be defined as the Baseline provided that this occurred prior to the single dose of study treatment within each Treatment Period.
- Unscheduled and repeated measurements will not be used in the descriptive statistics at timepoints after the single dose of study treatment in each Treatment Period.
- Unscheduled measurements performed for the ET Visit will be assigned to the EOS Visit and analyzed accordingly as an EOS Visit.

4.2 Primary endpoints analysis

This section includes both primary and sensitivity analyses of the primary endpoints.

4.2.1 Definition of endpoints

The primary endpoints are:

- Area under the plasma concentration-time curve from time 0 to infinity (AUC)
- Area under the plasma concentration-time curve from time 0 to time t (AUC_{0-t})
- Maximum (or peak) observed plasma concentration (C_{max})

Pharmacokinetic parameters will be determined by non-compartmental analysis in Phoenix WinNonlin using the PKS. Details of the PK parameter calculations are described in [Section 6.9](#).

The PK parameters of ZLP will be computed using the actual blood sampling timepoints.

4.2.2 Main analytical approach

The primary analysis to establish bioequivalence and sensitivity analyses are described in [Section 4.2.2.1](#) and [Section 4.2.2.2](#), respectively. Details of the standard reporting procedures of plasma concentrations and PK parameters are described in [Section 6.10](#). Study specific instructions for producing tables, figures, and listings for plasma concentrations and PK parameters are provided below.

All PK statistical analysis, summaries, and listings will be performed using the PKS.

For plasma concentrations:

- In the event that a study participant does not receive a full dose of ZLP in either one or both treatment periods, they will be excluded from the statistical summaries for the relevant periods.

For PK parameters:

- In the event that a study participant does not receive a full dose of ZLP in either one or both treatment periods, the study participant will be excluded from the primary analysis to establish bioequivalence, but will be included in a sensitivity analysis and statistical summaries for the Treatment Period in which they received a full dose.
- If a study participant withdraws early from either Treatment Period (before Day 3 for C_{max} or before Day 35 for AUC and AUC_{0-t}) the study participant's PK parameters for that Treatment Period will be excluded from the primary analysis to establish bioequivalence, the planned sensitivity analyses, and statistical summaries. Parameters associated with the primary endpoints will also be excluded from statistical summaries for that study participant.

4.2.2.1 Primary analysis to establish bioequivalence

The analysis of the primary endpoints will be used to establish the bioequivalence of ZLP-PK after a single sc injection with ZLP-PFS and ZLP-AI.

The primary analysis to determine if bioequivalence is established will use data from study participants who have evaluable primary PK endpoints for both treatments. Each primary PK endpoint will be analyzed separately. An analysis flag will be created to indicate whether the PK endpoint was included in the primary statistical analysis. Any values excluded will be flagged in the listings of the primary PK endpoints. Other analysis flags may be created for the sensitivity analyses.

Log-transformed PK parameters of AUC, AUC_{0-t} , and C_{max} will be analyzed using a mixed-effects model with period, treatment and sequence as fixed effects and study participant as a random effect. The ZLP-PFS device will be considered the reference treatment for the comparisons.

The least squares (LS) means and their associated 95% CIs for each treatment, and the difference in LS means and its 90% CI between the 2 treatments (ZLP-AI versus ZLP-PFS) will be estimated. All estimates will be back-transformed to provide geometric means and 95% CI for each treatment, and the ratio of geometric means (ZLP-AI/ZLP-PFS) and its 90% CI will also be provided. The point estimates and CIs for the ratios will be presented to 4 decimal places. Inter- and intra-participant variability of PK parameters will be derived from the results of this analysis. The intra-participant variability will be reported as CV.

4.2.2.2 Sensitivity analyses

The following sensitivity analyses will be carried out if required:

- If one or more study participants do not have evaluable primary PK endpoints for both Treatment Periods, an analysis using the same model as the primary analysis with the inclusion of Satterthwaite's correction for degrees of freedom will be carried out using data from study participants with evaluable PK endpoints in one or both Treatment Periods. (Sensitivity Analysis 1)
- If one or more study participants do not have evaluable primary PK endpoints for both Treatment Periods, an analysis using the same model as in the primary analysis will be carried out but will only include the study participants who have all three evaluable

primary PK endpoints (AUC, AUC_{0-t}, and C_{max}) in both Treatment Periods. (Sensitivity Analysis 2)

Other sensitivity analyses may be performed if necessary, and will be dependent on the PK data.

4.3 Secondary endpoints analysis

The analysis of the secondary endpoints will be used to evaluate the safety and tolerability of ZLP after a single sc injection with ZLP-PFS and ZLP-AI.

4.3.1 Definition of endpoints

The secondary endpoints are the occurrence of treatment-emergent serious adverse events (SAEs), treatment-emergent adverse events (TEAEs), and adverse device effects (ADEs, serious and nonserious) from Study Day 1 (post dose) up to the EOS or ET Visit.

4.3.2 Main analytical approach

All safety analyses will be performed using the SS. The secondary endpoints will be analyzed as detailed in Section 4.5.2.

4.4 Exploratory endpoints analysis

4.4.1 Safety and tolerability endpoints analysis

The objective of the exploratory endpoint is to further evaluate the safety and tolerability of ZLP after a single sc injection with ZLP-PFS and ZLP-AI.

4.4.1.1 Definition of endpoints

The exploratory endpoints are:

- Change from Baseline in clinical laboratory tests (hematology, clinical chemistry, and urinalysis)

4.4.1.2 Main analytical approach

All safety analyses will be performed using the SS. The safety endpoints above will be analyzed as detailed in Section 4.5.3.1.

4.4.2 Pharmacokinetic endpoints analysis

The objective of the exploratory endpoint is to further evaluate the PK of ZLP after a single sc injection with ZLP-PFS and ZLP-AI.

4.4.2.1 Definition of endpoints

The exploratory endpoints are:

- Terminal half-life (t_{1/2})
- Apparent plasma clearance (CL/F)
- Time to maximum observed concentration (t_{max})
- Apparent volume of distribution (V_d/F)

4.4.2.2 Main analytical approach

Pharmacokinetic analyses will be performed using the PKS.

The PK parameters $t_{1/2}$, CL/F, and V_z/F will be summarized by treatment using descriptive statistics as for the PK parameters described in Section 4.2.2. For the PK parameter t_{max} , only median, minimum, and maximum will be reported. Other PK parameters or diagnostics that support the derivation of the primary or exploratory PK endpoints, as defined in Table 1–1, will also be listed and summarized (e.g. AUC_{extr} , λ_z , t_{last} , and MRT [mean residence time]).

4.4.3 Device deficiency analysis

4.4.3.1 Definition of endpoints

The exploratory endpoints are:

- Device deficiencies as reported via the electronic case report form (eCRF)

4.4.3.2 Main analytical approach

The device deficiency analysis will be performed using the SS.

Device deficiencies will be listed by treatment sequence and their occurrence and incidence will be summarized by treatment if there are sufficient data.

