### **6.1.1 Devices**

The ZLP drug product will be supplied as:

- ZLP-PFS: A sterile, preservative-free aqueous solution prefilled into a syringe within a needle safety device. The ZLP-PFS is a single-integral, non-reusable drug-device combination product.
- ZLP-AI: A sterile, preservative-free aqueous solution prefilled into a syringe inside an autoinjector. The ZLP-AI-1mL is a single-integral, non-reusable drug-device combination product.

All Adverse Device Effects (serious and nonserious) and device deficiencies (including malfunction use error and inadequate labeling) for all devices, shall be documented and reported by the Investigator throughout the study (see Section 8.2.8) and appropriately managed by the Sponsor.

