### 10.7.3 Definition of device deficiency

Device deficiency definition
• A device deficiency is an inadequacy of a device with respect to its identity, quality, durability, reliability, safety, or performance. Device deficiencies include malfunctions, use errors, and inadequate labeling.

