3 POPULATIONS FOR ANALYSIS

The All Study Participants Set (ASPS) will consist of all study participants who signed the informed consent. This set includes screening failures and will be used for disposition and demographics of study participants. The ASPS will also be used for the listing of all adverse events (AEs).

The Randomized Set (RS) will consist of all study participants who are randomized. The RS will be used for disposition and demographics of study participants. Note: This set will only be produced if it differs from the Safety Set.

The Safety Set (SS) will consist of all study participants who are randomized and receive at least 1 dose of ZLP. In this context, 'dose of ZLP' includes the use of the device with the administration of the drug (either partial or full dose received). Study participants will be classified according to the treatment sequence in which they actually received the treatments. The SS will be used for all safety analyses.

The Pharmacokinetic Set (PKS) will consist of all study participants who are randomized, receive at least 1 dose of ZLP (defined as per SS above), and have at least 1 observable PK concentration measurement. The PKS will be used for analyses of PK endpoints. If a study participant in the PKS is missing concentrations at individual time points or these are otherwise unobservable, the study participant will be included in the PKS but those values will be omitted from the summaries of PK concentrations, as appropriate. Note that some study participants in the PKS may not have a complete set of PK parameters as some parameters may not be able to be calculated based on the PK concentrations collected.

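### Device deficiencies are analysed in the Safety Set, so a device that delivers no drug is missing from the deficiency outputs if the participant is never dosed by either device

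*SAP*

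**What the plan says.** The analysis set for device deficiencies is fixed in SAP 4.4.3.2: "The device deficiency analysis will be performed using the SS". The same section plans a listing by treatment sequence and, if the data suffice, a summary by treatment.

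Membership of that set is defined in SAP 3: "The Safety Set (SS) will consist of all study participants who are randomized and receive at least 1 dose of ZLP". The next sentence explains the term: "In this context, 'dose of ZLP' includes the use of the device with the administration of the drug (either partial or full dose received").

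Three further rules bear on the point:

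- SAP 4.3.2, for the secondary endpoint, which includes adverse device effects (ADEs): "All safety analyses will be performed using the SS".
- SAP 4.1.4: "Treatment assignment for the SS and PKS will be according to the actual treatment received". SAP 4.5.2 likewise attributes treatment-emergent adverse events (TEAEs) to the latest treatment the participant received.
- SAP 4.5.2 presents the adverse event listings, apart from one by-event listing, for the All Study Participants Set.

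On the protocol side, Section 10.7.3 defines the event without reference to drug delivery: "A device deficiency is an inadequacy of a device with respect to its identity, quality, durability, reliability, safety, or performance". Section 6.1.1 sets the recording duty: "All Adverse Device Effects (serious and nonserious) and device deficiencies (including malfunction use error and inadequate labeling) for all devices, shall be documented". Section 9.4.2.1 says deficiencies will be listed and names no analysis set.

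**The concern.** A deficiency is a property of the device, and failing to deliver is one way for a device to be deficient. Entry to the set in which deficiencies are analysed, however, depends on some drug having been delivered. Membership thus depends partly on the outcome being measured: a partial failure always stays in, while a complete failure can fall out together with the participant.

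Evaluating device deficiencies is a stated exploratory objective, and ADEs are part of the secondary endpoint. The study compares two delivery devices with about 14 uses of each, so one missing failure changes what the report shows about a device. A second, related problem is attribution. Where no drug came out, a rule based on treatment received does not point to the device that was attempted.

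**Working it through.** There is no stated figure to reproduce. The check applies the SAP rules to each possible case.

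**Step 1. Who is in the Safety Set.** Membership is decided per participant across both periods (SAP 3), and each participant is planned to receive one injection with each device (Protocol 4.1). The cases with at least one zero-delivery failure are:

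| Period 1 | Period 2 | In Safety Set | Zero-delivery failures | Missing from deficiency outputs |
|---|---|---|---|---|
| delivered | nothing | yes | 1 | 0 |
| nothing | delivered | yes | 1 | 0 |
| nothing | nothing | no | 2 | 2 |
| nothing | not attempted | no | 1 | 1 |

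Failures are lost in two of the four cases, both of which begin with a failed Period 1 device.

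**Step 2. Which uses are exposed.** With 7 participants per sequence (SAP 1.2), 7 of the 14 planned auto-injector uses fall in Period 1 (sequence BA), as do 7 of the 14 planned syringe uses (sequence AB). The exposure is symmetric. A Period 2 failure is lost only if the Period 1 device also delivered nothing.

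**Step 3. Whether another output recovers the deficiency.** The Randomized Set serves disposition and demographics. The All Study Participants Set serves those and the adverse event listing (SAP 3). The exposure listing is in the Safety Set (SAP 4.5.1). A malfunction without an adverse event therefore appears in no planned device-deficiency output. An ADE from the attempt is in the adverse event listing but not in the Safety Set tables.

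**Step 4. Attribution.** Take sequence AB: the syringe delivers in Period 1 and the auto-injector delivers nothing in Period 2. The participant is in the Safety Set. The latest treatment received is still the syringe, so an ADE from the auto-injector attempt is credited to the syringe. In sequence BA the error runs the other way. This route needs no withdrawal.

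**Step 5. Size, as illustration only.** If one Period 1 auto-injector failure ends in withdrawal undosed:

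- on attempts: 1/14 = 7.1%;
- in the Safety Set: 0/13 = 0%.

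The documents give no failure rate. Assume a zero-delivery rate q per device use, equal for both devices and independent between periods, and let r be the share of participants who leave after a Period 1 failure. Other dropout is ignored.

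- Failures per participant: q + (1 − qr)q.
- Failures lost per participant: qr + 2q²(1 − r).
- Chance that at least one of 14 participants is lost in this way: 1 − (1 − [qr + q²(1 − r)])^14.

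| q (assumed) | Share lost, r = 1 | Chance, r = 1 | Share lost, r = 0 | Chance, r = 0 |
|---|---|---|---|---|
| 1% | 50.3% | 13.1% | 1% | 0.14% |
| 2% | 50.5% | 24.6% | 2% | 0.56% |
| 5% | 51.3% | 51.2% | 5% | 3.4% |

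The result depends almost wholly on r, that is, on what happens after a failed Period 1 attempt. The documents do not state this.

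**The case against.** The strongest reply is that the route is narrow and the failure would not go unseen. Much of that is right.

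- A lost failure needs a participant never dosed by either device. Device failure is not among the withdrawal events listed in Protocol 7.2, and SAP 4.2.2 plans for participants who lack a full dose in one period and keeps their data from the other.
- The failure would partly surface elsewhere. SAP 6.3 counts randomised participants who received no study treatment and lists reasons for study termination. SAP 6.13 says dosing deviations will be described in the study report. Under the protocol, deficiencies go to the sponsor within 24 hours (8.2.8.3), and product quality complaints are investigated (9.4.2.1).
- The deficiency endpoint is exploratory and descriptive, and its summary is conditional on sufficient data. A printed 0/13 may never exist.
- A deficiency record concerns a specific device, so in practice a programmer could place it correctly.

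These points limit the consequence but do not repair the rule, since none of them puts the event into the planned deficiency listing. It may also be said that the word for inclusion in SAP 3 is not exclusive, so a zero-delivery attempt could count as a dose. If that is intended, the SAP should say so. Otherwise membership would be decided after the failure is known.

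Stronger readings are tempting but unsupported. A reader might infer that ADEs from a failed attempt vanish from the listings. They do not, because those listings use the All Study Participants Set. A reader might infer a bias in favour of the auto-injector, but the same route applies to the syringe in sequence AB. A reader might see a contradiction with the protocol. However, Protocol 6.1.1 governs documentation and reporting, and 9.4.2.1 names no set, so the SAP filled a gap.

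**Conclusion.** The point holds in a limited form. As written, a zero-delivery failure is omitted from the planned deficiency listing and summary when the participant never receives zilucoplan from either device. An ADE from such an attempt is listed but left out of the summaries. Within the Safety Set, the treatment-received rule read literally assigns an ADE from a failed Period 2 device to the other device.

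The direct route covers Period 1 uses only: 7 planned uses of each device, with no second delivery. How often it would occur cannot be derived from the documents, and the 1/14 against 0/13 contrast and the assumed rates are illustrations. The conclusion rests on reading the dose definition as excluding a use with no drug delivered. The bioequivalence analysis is not affected.

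**What to change.** Amend SAP 4.4.3.2, with matching wording in 4.5.2, before database lock:

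1. Analyse device deficiencies in all randomised participants on whom a study device was used or attempted, whether or not drug was delivered.
2. Attribute deficiencies and ADEs to the device used or attempted, not to the treatment received.
3. Use the number of devices used or attempted, per device type, as the denominator.
4. Summarise ADEs in the same set.

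Leave the Safety Set unchanged for drug TEAEs.

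The cost is two or three sentences and one analysis flag. Deficiencies are already reported in the eCRF, and Protocol 6.2.1 already requires records of used, partially used and unused product, which should supply the denominator. No new data collection is needed.
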